### 6.3.2. Intent-to-Treat (ITT) Population

The ITT Population will consist of all randomized subjects regardless of whether or not they receive study product or placebo. ITT analysis will be performed based on the treatment that a subject is randomized to receive.

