### 8.1.3. Benefit to Risk Profile Analysis Using DOOR

Each subject will have a composite DOOR rank assigned to them based on the presence or absence of SAEs related to study product and the reduction in  $\log_{10} P. aeruginosa$  CFU/mL. DOOR rank will be determined according to the definition in Section 3.3.1.

DOOR probability, which is defined by:

$$DOOR\ probability = Pr[DOOR_2 > DOOR_1] + \frac{1}{2} Pr[DOOR_2 = DOOR_1],$$

will be estimated using the Wilcoxon-Mann-Whitney statistic, correcting for ties and divided by the product of the placebo and IV bacteriophage group sample sizes, where

- DOOR2 and DOOR1 are the DOOR for IV bacteriophage and placebo arms, respectively
- Pr[DOOR2 > DOOR1] is the probability of a DOOR from IV bacteriophage dose being more desirable than a DOOR from placebo, and
- Pr[DOOR2 = DOOR1] is the probability that the DOOR outcomes in IV bacteriophage and placebo are the same.

The corresponding two-sided 95% CI will be calculated using the method described in Halperin et al. [2] for the incorporation of IPW described in Section 8.1.3.1. Note that all CIs are two-sided.

The 95% CI by Halperin et al. [2] will be calculated in the following manner:

- $n_1$ : number of subjects in ITT population randomized to placebo
- $n_2$ : number of subjects in ITT population randomized to IV bacteriophage
- $W$ : Wilcoxon-Mann-Whitney statistic for ordinal outcomes, corrected for ties
- $\zeta$ : DOOR probability
- $\hat{\zeta}$ : An unbiased estimator of  $\zeta$ ,  $\hat{\zeta} = W/(n_1 n_2)$
- $V$ : The variance of the DOOR probability. Correcting for ties, the formula for the variance of the DOOR Probability, as described in Halperin et al. [2], is:

$$\hat{V} = Var(\zeta) = \frac{1}{n_1 n_2} [n_1 + n_2 + 1 - (n_1 + n_2 - 2)\theta] \zeta (1 - \zeta)$$

where

$$\theta = \frac{[(n_1 + n_2 - 2)\zeta - (n_2 - 1)A - (n_1 - 1)B]}{(n_1 + n_2 - 2)\zeta(1 - \zeta)}$$

To obtain an estimator  $\hat{\theta}$  of  $\theta$ , the following formulas will be used for A and B, respectively:

$$\hat{A} = \hat{A}_1 - \frac{1}{n_2 - 1} \sum_{i=1}^{D-1} p_{1i} \left[ q_{2i} \sum_{j=i+1}^D p_{2j} - \left( \sum_{j=i+1}^D p_{2j} \right)^2 \right] - \frac{1}{4(n_2 - 1)} \sum_{i=1}^D p_{1i} p_{2i} q_{2i}$$

where

$$\hat{A}_1 = \sum_{i=1}^{D-1} p_{1i} \left[ \sum_{j=i+1}^D p_{2j} + \frac{p_{2i}}{2} \right]^2 + \frac{p_{1D} p_{2D}^2}{4}$$

and

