$$\hat{B} = \hat{B}_1 - \frac{1}{n_1 - 1} \sum_{j=2}^D p_{2j} \left[ q_{1j} \sum_{i=1}^{j-1} p_{1i} - \left( \sum_{i=1}^{j-1} p_{1i} \right)^2 \right] - \frac{1}{4(n_1 - 1)} \sum_{j=1}^D p_{2i} p_{1i} q_{1i}$$

where

$$\hat{B}_1 = \sum_{j=2}^D p_{2j} \left[ \sum_{i=1}^{j-1} p_{1i} + \frac{p_{1j}}{2} \right]^2 + \frac{p_{11}^2 p_{21}}{4}$$

In the equations for A and B above, D is the number of DOOR outcome ranks in the dataset;  $p_{1i}$ , for  $i = 1, 2, \dots, D$ , represents the proportion of subjects randomized to placebo with the  $i^{\text{th}}$  rank category of DOOR;  $p_{2j}$ , for  $i = 1, 2, \dots, D$ , represents the proportion of subjects randomized to IV Bacteriophage with the  $j^{\text{th}}$  value of DOOR; and  $q = 1 - p$  in general.

Additionally, the equation for an unbiased estimate of  $\zeta(1 - \zeta)$  is given by:

$$\frac{(n_1 n_2 - n_1 - n_2 + 2)\hat{\zeta} - n_1 n_2 \hat{\zeta}^2}{(n_1 - 1)(n_2 - 1)} + \frac{\hat{A}}{n_1 - 1} + \frac{\hat{B}}{n_2 - 1}$$

After substituting the values of A, B and  $\zeta(1 - \zeta)$  in the equation  $\theta$  to obtain an estimate  $\hat{\theta}$  of  $\theta$ ,  $\theta$  is defined as follows: If  $\hat{\theta} < 0$  then  $\theta = 0$ , if  $\hat{\theta} > 1$  then  $\theta = 1$ , otherwise  $\hat{\theta} = \theta$ .

We now compute the pivotal quantity  $Z_H^2 = (\hat{\zeta} - \zeta)^2 / \hat{V}$ .

$$\gamma = (n_1 + n_2 - 1) - (n_1 + n_2 - 2)\hat{\theta}$$

The CI is obtained as the solution set in  $\zeta$  of the quadratic inequality:

$$n_1 n_2 \frac{(\hat{\zeta} - \zeta)^2}{\gamma \zeta (1 - \zeta)} \leq \chi^2(1, 1 - \alpha)$$

Let,  $C = \gamma \chi^2(1, 1 - \alpha) / (n_1 n_2)$ . The CI is given as:

$$\frac{C + 2\hat{\zeta} \pm [C^2 + 4C\hat{\zeta}(1 - \hat{\zeta})]^{1/2}}{2(C + 1)}$$

The superiority of IV bacteriophage vs placebo is concluded if the lower bound of the 95% CI for the DOOR probability is larger than 50%.

Due to the presence of missing data, IPW will be used to handle missing data. For the sensitivity analysis of DOOR, IPW method will be used (see Section 8.1.3.1).

The DOOR will be analyzed as follows:

- DOOR probability with corresponding 95% CI calculated using the method described in Halperin et al. [2] calculated using the greatest reduction in *P. aeruginosa* CFU/mL by Day 8 (Table 26).
- DOOR categories distribution by treatment group through Day 8 + 3 (Table 28).

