#### 8.1.3.1. Intention-to-Treat (ITT) Analysis of DOOR using Inverse Probability Weighting

Intention-to-treat analysis requires that all randomized subjects be included in the analysis. However, missing data is prone to happen in clinical trials due to missing scheduled visits or loss to follow-up for example. In this case, analysis that is only based on complete data may be biased if the excluded subjects are systematically different from those included. IPW is one approach commonly used to reduce this bias under a MAR assumption. This is achieved by weighting complete cases with the inverse of their probability of being a complete case. While subjects missing the DOOR are excluded from the analysis per se, they may still inform the fitting of the logistic regression model used to provide predictions of the probability of completeness which are used to calculate the weights.

Specifically, let  $Y_i$  represent the outcome of interest (DOOR),  $X_i$  represent the covariates of interest,  $Z_i$  represent any other variables measured in the data but not used in the analysis model. For the IPW approach, we first define the missingness model to estimate the weights ( $w_i$ ) using a logistic regression model with outcome  $L$  and covariates taken from set  $(X, Z)$  where  $L_i$  is defined as 1 if DOOR data is complete (not missing) and 0 otherwise. Through this model, we obtain the fitted probabilities of each subject being complete, denoted as  $\pi_i$ .

The DOOR probability can then be calculated using DOOR at Day 8 as the outcome following the algorithm below:

1. Name DOOR from the group that received placebo “sample 1” and the DOOR score ranks from the group that received IV bacteriophage “sample 2”. Rename weights from sample 1 as  $w_{1i}$  and weights from sample 2 as  $w_{2i}$ .
2. Take the first observation in sample 2. If an observation in sample 2 has a smaller DOOR score rank than an observation in sample 1, then that observation in sample 2 gets an indicator of value of 1. Otherwise, if the observation in sample 2 is equal to the observation in sample 1, the observation in sample 2 gets an indicator value of  $\frac{1}{2}$ .
3. Let  $\pi_{1i}$  be the fitted probability of being complete for each observation in sample 1 and  $\pi_{2i}$  be the fitted probability for being complete for each observation in sample 2 obtained from the logistic regression model with an indicator for having non-missing DOOR score rank as the outcome.

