## 1. INTRODUCTION

After an interim analysis the optimal dose for Stage 2b was selected on 02FEB2024. The decision was unanimous among Phage Advisory Group (PAG) members and was made based on the benefit to risk profile that considered both the safety profile of bacteriophage preparations as well as the observed reductions in *P. aeruginosa* colony forming units (CFU)/mL. During review of the interim data the issue of several subjects having undetectable *P. aeruginosa* colony counts came to light, where the lower detection limit was  $10^4$  CFU/mL per colony morphology for Stage 2a. Due to the data collection practices prior to the interim analysis, if *P. aeruginosa* was not recovered in a sputum sample with MALDI TOF confirmation of genus/species then null results were entered for the colony counts. As there was no detectable result (i.e. missing in the dataset) entered for the colony counts for these samples, they were treated as missing during data analysis.

This detection limit issue was unexpected at the time of planning, and the statistical analysis plan (SAP, version 1.0, dated 14NOV2023) does not address how to handle data censored due to the limit of detection. Under this scenario the exact value of an observation is unknown but is known to be below the lower limit of detection. Of the 32 subjects in the interim analysis, 3 had undetectable *P. aeruginosa* colony counts at baseline and 2 had undetectable *P. aeruginosa* colony counts at every time point post-baseline. As they were treated as missing for the interim analysis, a change from baseline was not calculable for these 5 subjects and they did not contribute information to the two primary analyses, i.e., change from baseline and the Desirability of Outcome Ranking (DOOR). These subjects were still analyzed for safety outcomes that factored into the dose selection decision.

This document describes the planned analyses as related to undetectable results. Because an undetectable result may or may not be a valid result (i.e. the sample did not contain sputum), both an analysis employing imputation and a sensitivity analysis will be considered where undetectable is treated as missing to both match the assumption that was used during the interim analysis and to explore the robustness of the assumption that all undetectable results are valid.

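### SAP 8.1.3 divides the unweighted DOOR win count by randomized ITT pairs, so every missing DOOR lowers that estimate; the IPW estimate is not lowered, but its interval lacks a defined n

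*SAP*

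**What the plan says.** SAP 8.1.3 estimates the DOOR probability by the tie-corrected Wilcoxon-Mann-Whitney statistic W, "divided by the product of the placebo and IV bacteriophage group sample sizes". For the Halperin method, n1 is the "number of subjects in ITT population randomized to placebo" and n2 the "number of subjects in ITT population randomized to IV bacteriophage". The rank proportion p1i "represents the proportion of subjects randomized to placebo with the" i-th category, and p2j is worded alike for bacteriophage. The estimator W/(n1 n2) is described as unbiased. The same n1 and n2 enter A, B, theta, gamma and C, and superiority is read from whether the lower 95% limit exceeds 50%.

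SAP 6.3.2 makes the ITT population "all randomized subjects regardless of whether or not they receive study product or placebo". Neither 3.3.1 nor 8.1.3 gives a rank to a subject whose reduction cannot be computed.

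SAP 8.1.3.1 gives a second estimator by inverse probability weighting: "While subjects missing the DOOR are excluded from the analysis per se", and the weighted wins are divided by the sum of the pair weights. Its interval is Halperin's with the weights incorporated, and n1 and n2 are not defined again.

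The SAP is not consistent about the role of IPW. Section 6.5 makes it a sensitivity analysis, 8.1.3.1 makes it the primary DOOR analysis, and the end of 8.1.3 says both. Table 26 and addendum Tables 14 and 15 print the result with and without IPW side by side.

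**The concern.** W can count only pairs in which both subjects have a DOOR, but it is divided by all pairs of randomized subjects. Each missing DOOR, in either arm, then acts as a set of lost comparisons for bacteriophage. DOOR is a primary endpoint read against a fixed 50% threshold, so loss of data could look like loss of effect, or like harm. Two columns of one table would rest on incompatible denominators and could disagree for no substantive reason. If a programmer corrects only the point estimate, the interval still claims subjects who were not observed.

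**Working it through.** **The plan's own precision figure.** Protocol 10.2 gives 51% to 89% for a true DOOR probability of 70% with 20 per arm. Using the no-ties null variance, SE = sqrt((20+20+1)/(12 × 20 × 20)) = 0.0924, and 0.70 ± 1.96 × 0.0924 = 51.9% to 88.1%. That is within one point of each stated limit; a t quantile on 38 df gives 51.3% to 88.7%. The figure assumes that all 20 per arm have a DOOR.

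**The algebra.** Let m1 and m2 be the subjects with a DOOR. Then

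W/(n1 n2) = [W/(m1 m2)] × (m1/n1) × (m2/n2).

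The first factor is the observed DOOR probability. The other two are the completeness rates.

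**Worked example (illustrative data).** There are 20 randomized and 18 observed per arm. Ranks 3/2/1 are 13/4/1 on placebo and 6/6/6 on bacteriophage.

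- Rank 1 on bacteriophage: 6 × (17 + 0.5) = 105
- Rank 2: 6 × (13 + 2) = 90
- Rank 3: 6 × 6.5 = 39
- W = 234

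Halperin interval coded from 8.1.3, with ranks ordered worst to best and gamma as printed:

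| Denominators | Estimate | 95% CI |
|---|---|---|
| Observed: n = 18, proportions over 18 | 234/324 = 0.722 | 0.550 to 0.847 |
| As printed: n = 20, proportions over 20 | 234/400 = 0.585 | 0.411 to 0.740 |
| Point estimate over observed pairs, n = 20 in the interval | 0.722 | 0.560 to 0.842 |

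The ratio of the first two estimates is 0.585/0.722 = 0.81 = (18/20)². In the third row the width is 0.282 against 0.297, about 5% too narrow. That row is the IPW result if randomized n is kept: the pseudocode models completeness on treatment alone, so weights are constant within arm and the IPW estimate equals the complete-case value. In the with/without table this dataset would show 0.722 beside 0.585.

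**Range over missingness.** The plan gives no rate. Assume placebo ranks 1/2/3 of 10/20/70%, bacteriophage 35/30/35% (true DOOR probability 0.695) and equal missingness, 20 per arm:

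| Missing per arm | As printed | Observed n |
|---|---|---|
| 1 | 0.627 (0.455 to 0.772) | 0.695 (0.525 to 0.824) |
| 2 | 0.563 (0.391 to 0.721) | 0.695 (0.520 to 0.827) |
| 3 | 0.502 (0.335 to 0.669) | 0.695 (0.515 to 0.830) |

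The arm does not matter to the point estimate. With 25 per arm and 3 missing on one side only, 0.695 × 22/25 = 0.612 whichever side it is.

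In simulation (6,000 runs, 20 per arm, missing completely at random), the lower limit exceeds 0.50 in 29% of trials as printed against 63% with observed n at 5% missing, and in 10% against 60% at 10% missing. With identical arms and 10% missing, the printed version puts the upper limit below 0.50 in 22% of trials, against about 2%.

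**IPW interval with randomized n.** It is 2.5% too narrow with 1 of 20 missing per arm and 10% too narrow with 4 of 20. Simulated coverage is about 94.7% down to 93% over 5% to 15.6% missing. At 15.6% missing, the false superiority rate is 3.6% to 3.7%, against about 2% to 2.5%.

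**The case against.** The strongest reply is that 8.1.3 is written in complete-data notation. It opens by giving every subject a rank, and missingness is handled separately in 8.1.3.1. Read literally, the rank proportions in the example sum to 0.90 and the estimator is not unbiased as claimed, so a programmer would probably use observed counts, and the gap between adjacent columns would expose a slip. That lowers the chance of harm. It does not change the definitions, which are explicit and give a wrong answer when followed.

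Other limits stand in full, and each rules out a stronger reading:

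- **That every DOOR output is pulled down.** The IPW estimate, which 8.1.3.1 calls primary, is not. Table 31's notes leave missing data out of the cumulative counts, Table 33 counts subjects with sputum collected, and 6.1 bases percentages on non-missing data. The point-estimate problem is confined to the columns without IPW in Tables 26 and 29 and addendum Tables 14, 15, 18 and 19, and to addendum Table 30, whose note mentions no weighting.
- **That the interim rate of 5/32 (16%) applies to the primary analysis.** The addendum says that "a change from baseline was not calculable for these 5 subjects", but because results were undetectable, and across all four Stage 2a arms. Undetectable results are now substituted at the limit of detection in the primary analysis. The rate bears only on the sensitivity analysis that treats them as missing.
- **That withdrawal means no DOOR.** A subject with a baseline and any post-infusion count by Day 8 can still be ranked, and undosed subjects may be replaced.
- **That the lower limit in the example falls to about 0.31.** That needs proportions over 18 combined with W/(20 × 20), a mixture printed nowhere. The printed definitions give 0.411.

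**Conclusion.** The rule is wrong as written for the unweighted DOOR estimate and its interval. The bias is downward for any missing DOOR in either arm, by the product of the completeness rates: 0.81 at 10% missing per arm, enough in the example to reverse the superiority reading. The direction follows from the algebra alone. The size depends on a missingness rate that the documents do not give, and the simulated figures rest on assumed rank distributions and equal, completely random missingness.

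For IPW only the interval is exposed, modestly and in the other direction. A reader might conclude that the primary DOOR result is biased; the documents do not settle that, because 6.5, 8.1.3 and 8.1.3.1 disagree on which estimator is primary. The sensitivity analysis treating undetectable results as missing is the most exposed, as is addendum Table 30: its cells vary the share of undetectable results left as missing, so the completeness factor would change from cell to cell and mix with the effect being examined.

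**What to change.** In SAP 8.1.3, define n1 and n2 as the ITT subjects in each arm with a non-missing DOOR for the outcome and time point analysed, and p1i and p2j as proportions of those subjects. Use these counts in zeta-hat, A, B, theta, gamma and C for all Halperin intervals, and state in 8.1.3.1 that the IPW interval uses them too. Carry the definitions into the addendum. Keep the randomized N as a displayed figure only, in line with 6.1 and the notes to Tables 31 and 33. Reconcile 6.5, 8.1.3 and 8.1.3.1 so that one DOOR estimator is named as primary.

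The cost is a few definitions and one consistent statement of role. Intervals are slightly wider than with the randomized n (0.297 against 0.282 in the example), which reflects the data observed.

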10 STATISTICAL CONSIDERATIONS

10.1 Study Hypotheses

The study does not include formal hypothesis testing for the three primary endpoints.

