## 6. GENERAL STATISTICAL CONSIDERATIONS

### 6.1. General Principles

All continuous variables will be summarized using the following descriptive statistics: n (non-missing sample size), mean, standard deviation (SD), median, quartiles, maximum, and minimum. The frequency and percentages (based on the non-missing sample size) of observed levels will be reported for all categorical measures. In general, all data will be listed, sorted by treatment and subject, and when appropriate by visit number within subject.

All safety summary tables and figures will be summarized by the following treatment groups in the following order:

- $4 \times 10^7$  PFU dose
- $4 \times 10^8$  PFU dose
- $4 \times 10^9$  PFU dose
- Placebo

The safety analysis in this SAP will include subjects from Stage 1, Stage 2a, and Stage 2b.

All microbiological activity and benefit to risk analyses, including the interim analysis, will be summarized by the following treatment groups in the following order:

- IV Bacteriophage Selected Dose
- Placebo

with “IV Bacteriophage Selected Dose” being replaced with the selected IV Bacteriophage dose found in the interim analysis, described in Section 8.3. The ‘IV Bacteriophage Selected Dose’ group will include subjects from Stage 2a and Stage 2b who received the selected IV bacteriophage dose. The ‘Placebo’ group will include subjects from Stage 2a and Stage 2b who received the placebo.

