## 6.8. Multiple Comparisons/Multiplicity

This exploratory study does not include formal hypothesis testing for any of the primary endpoints, therefore no adjustments for multiple testing are planned.

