## 8. MICROBIOLOGICAL ACTIVITY AND BENEFIT TO RISK PROFILE EVALUATION

All variables in the microbiological activity and benefit to risk profile analyses will be listed by subject. Data will be summarized by treatment group. Continuous variables will be summarized with the number of observations, mean, median, SD, quartiles, minimum, and maximum. Categorical variables will be summarized by number and percent in each category. All microbiological activity and benefit to risk profile analyses will be performed using the ITT population.

This study does not include formal hypothesis testing for any of the primary endpoints, and instead relies on CIs for conclusions of treatment effects.

All microbiological activity and benefit to risk profile tables and figures will compare all subjects receiving placebo to all subjects receiving the selected dose of IV bacteriophage chosen from the interim analysis.

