**Table 26: DOOR Probability and 95% Confidence Interval by Day 8 – ITT Population, Stage 2a and 2b**

Subjects With Non-missing DOOR – n (%)	Subjects With Missing DOOR – n (%)	DOOR Probability With IPW a (95% CI) b	DOOR Probability Without IPW c (95% CI) b
x (x)	x (x)	x.xx (x.xx, x.xx)	x.xx (x.xx, x.xx)

aProbability of more desirable DOOR in IV bacteriophage + 0.5 (probability of equal DOOR) using the greatest reduction in *P. aeruginosa* CFU/mL by Day 8. This analysis uses IPW to handle the impact of missing values of DOOR.

b95% CI calculated using the method in Halperin et. al Superiority of IV bacteriophage vs. placebo is concluded if the lower bound of the 95% CI for the DOOR probability is above 0.5.

cThis calculation does not use inverse probability weighting to handle missing DOOR values.

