**Table 29: Subgroup Analysis of DOOR at Day 8 – ITT Population, Stage 2a and 2b**

[Implementation note: ‘Organism X’ will be replaced with any organisms recovered on sputum cultures with one yes/no row for each organism.]

Subgroup	Subjects With Non-missing DOOR – $n_b$ (%)	Subjects With Non-missing DOOR – $n_p$ (%)	Subjects With Missing DOOR – $n_b$ (%)	Subjects With Missing DOOR – $n_p$ (%)	DOOR Probability With IPW a (95% CI) b	DOOR Probability Without IPW c (95% CI) b
Susceptible to Bacteriophages – Yes	x (x)	x (x)	x (x)	x (x)	x.xx (x.xx, x.xx)	x.xx (x.xx, x.xx)
Susceptible to Bacteriophages – No	x (x)	x (x)	x (x)	x (x)	x.xx (x.xx, x.xx)	x.xx (x.xx, x.xx)
Presence of Co-infection with Organism X – Yes	x (x)	x (x)	x (x)	x (x)	x.xx (x.xx, x.xx)	x.xx (x.xx, x.xx)
Presence of Co-infection with Organism X – No	x (x)	x (x)	x (x)	x (x)	x.xx (x.xx, x.xx)	x.xx (x.xx, x.xx)

Notes:  $n_b$ =number of subjects in the ITT population in Stage 2a and 2b who received IV bacteriophage within the subgroup category.  $n_p$ =number of subjects in the ITT population who received placebo within the subgroup category. Denominator for percentages is the total number of IV bacteriophage subjects in the ITT population for  $n_b$  and the total number of placebo subjects in the ITT population for  $n_p$ .

aProbability of more desirable DOOR in IV bacteriophage arm + 0.5 (Probability of Equal DOOR) using the greatest reduction in *P. aeruginosa* CFU/mL by Day 8. This analysis uses IPW to handle the impact of missing values of DOOR.

b95% CI calculated using the method in Halperin et. al. Superiority of IV bacteriophage vs placebo is concluded if the lower bound of the 95% CI for the DOOR probability is above 0.5.

cThis calculation does not use inverse probability weighting to handle missing DOOR values.

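### The plan disclaims formal testing, and therefore any adjustment, yet concludes superiority from unadjusted 95% CIs for the DOOR probability, overall and by footnote in exploratory subgroup rows, with the dose-selection subjects pooled in

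*SAP*

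**What the plan says.** **The disclaimer.** Protocol 10.1: "The study does not include formal hypothesis testing for the three primary endpoints". SAP 6.8: "This exploratory study does not include formal hypothesis testing for any of the primary endpoints, therefore no adjustments for multiple testing are planned". The absence of testing is the only reason given for not adjusting.

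**The decision rule.** SAP 8.1.3: "superiority of IV bacteriophage vs placebo is concluded if the lower bound of the 95% CI for the DOOR probability is larger than 50" per cent. SAP 8.1.3.1 repeats it for the inverse-probability-weighted (IPW) analysis. The Table 26 footnote reads "Superiority of IV bacteriophage vs. placebo is concluded if the lower bound of the 95% CI for the DOOR probability is above 0.5". The same footnote is attached to the CI columns of the subgroup table (Table 29): "Superiority of IV bacteriophage vs placebo is concluded if the lower bound of the 95% CI for the DOOR probability is above 0.5". Subgroup rows are susceptible yes/no and co-infection yes/no, where the organism placeholder "will be replaced with any organisms recovered on sputum cultures with one yes/no row for each organism". The addendum, written after the interim analysis, keeps the footnote in its Tables 14, 15, 18 and 19.

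**Wording on both sides.** SAP 8 says the study does no formal testing "and instead relies on CIs for conclusions of treatment effects". Protocol 10.2 justifies 20 per arm by a lower limit above 50%. Protocol 10.4.2 defines a null hypothesis of a DOOR probability of at most 50% at the final analysis. SAP 6.6 and 8.3 also speak of rejecting the null hypothesis.

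**Selection and pooling.** One of three doses is chosen on Stage 2a data. The addendum's introduction says the choice weighed safety and the observed colony-count reductions. In the final analysis the selected-dose "group will include subjects from Stage 2a and Stage 2b who received the selected IV bacteriophage dose", and placebo is pooled in the same way.

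**The concern.** A yes/no conclusion drawn from one confidence limit is a test, whatever it is called. The reason given for not adjusting therefore fails wherever the superiority rule applies. Two features push the error in one direction:

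- The Stage 2a subjects who helped their dose win are counted again in the final comparison. Colony-count reduction informs the choice and also defines DOOR ranks 1 to 3.
- The same rule is attached to every subgroup row.

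At stake is a superiority statement, possibly for a single subgroup, that Protocol 10.1 says the study is not set up to make. There is also a pooled estimate carrying no caution about selection, which could be used to size a follow-on trial.

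**Working it through.** **1. The plan's own figure.** Protocol 10.2 gives 51% to 89% for a true DOOR probability of 70% with 20 per arm. With the Wilcoxon-Mann-Whitney null variance, SE = √[(n₁+n₂+1)/(12n₁n₂)] = √(41/4800) = 0.0924. Then 0.70 ± 1.96 × 0.0924 gives 51.9% to 88.1%, and the t quantile on 38 df (2.024) gives 51.3% to 88.7%, which rounds to the stated limits. The design calculation reproduces, and it uses the 50% benchmark.

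**2. What the rule amounts to.** SAP 8.1.3 makes all CIs two-sided. A lower 95% limit above 50% is therefore a one-sided 2.5% test of a DOOR probability of at most 50%.

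**3. Reused data.** 8/20 = 40% of each final arm at the planned size, and 8/25 = 32% at the maximum.

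**4. False overall superiority if all doses are inert.** The interval is the one in SAP 8.1.3, with γ = (n₁+n₂−1) − (n₁+n₂−2)θ. Each simulated trial has 8 subjects on each of three doses and placebo, selects a dose, adds 12 or 17 per arm and pools. Everything below is assumed, because the documents give no DOOR rates and no mechanical selection rule.

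- *Rank model:* six distributions of ranks 1/2/3/4, from 5/15/79/1% to 33/33/33/1%; 60,000 runs each.
- *Count model:* log₁₀ CFU with subject mean 6.5 or 7.5 (SD 1.2), within-subject SD 0.4 to 1.0, detection limit 10⁴, and the addendum's 3/32 undetectable at baseline and 2/32 at every later visit. Undetectable results are missing at the interim and set to 10⁴ at the end; 40,000 runs each.
- *Looser selection:* highest interim DOOR after adding noise of SD 0.1 or 0.2, as a stand-in for committee judgement.

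| Model | Selection | False superiority | Mean shift (points) |
|---|---|---|---|
| Rank | Random | 2.0-2.5% | 0 |
| Rank | Looser | 2.6-4.1% | +0.7 to +2.3 |
| Rank | Highest interim DOOR | 3.7-4.9% | +2.0 to +3.3 |
| Count | Random | 1.7-2.5% | none expected |
| Count | Looser | 2.1-3.8% | +0.4 to +2.0 |
| Count | Largest mean log₁₀ reduction | 2.5-4.1% | +0.9 to +2.4 |
| Count | Highest interim DOOR | 3.0-4.4% | +1.4 to +2.8 |

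With an assumed unblinded increase from 20 to 25 per arm, the rank model gives 2.7-4.2% (looser) and 3.9-5.0% (mechanical). Stage 2b alone gives 1.3-2.5%, with bias within 0.1 point. Two-sided coverage stays at 94-97%.

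**5. Shift against precision.** At an estimate of 70%, the SAP formula with four tied ranks gives about 53-54% to 82-83% at 20 per arm, a half-width of 14-15 points.

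**6. Subgroup rows.** The overall row plus four rows (one organism) makes five distinct comparisons. Subgroup prevalences of 50/50, 70/30 and 70/50% are assumed, unrelated to outcome; rows need at least 3 subjects per arm; 40,000 runs each. At least one false superiority statement occurs in 4.5-8.7% (random selection), 6-12% (looser) and 8-14% (mechanical). For reference, five independent looks would give 1 − 0.975⁵ = 11.9%.

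**7. Counting intervals.** The addendum attaches the rule to 2 + 2 + 8 + 8 = 20 intervals (Tables 14, 15, 18, 19). Half are with/without-IPW pairs. The pseudocode's missingness model contains treatment only, so each pair weight w = 1/(π₁π₂) is the same constant, and Σ(w × indicator)/Σw equals the unweighted estimate. Tables 15 and 19 are sensitivity repeats. The distinct comparisons number five.

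**Not modelled:** the IPW-weighted CI, whose formula SAP 8.1.3.1 does not give, and outcome-dependent missingness at the final analysis.

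**The case against.** The strongest reply is that 50% is not a stray SAP sentence. Protocol 10.2 and 10.4.2 and SAP 6.6 and 8.3 use it as a design or interim benchmark, and SAP 8 expressly plans to draw conclusions from CIs. This stands in part. A reader might infer that the superiority rule departs from an otherwise purely descriptive plan; the documents do not support that, because they are divided. It does not remove the conflict with Protocol 10.1 and SAP 6.8, but it does mean that deleting the rule alone would leave other passages inconsistent.

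A reader might also take the 20 footnoted intervals as 20 chances of a false claim. They are not, for the reasons in step 7.

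The subgroup rule appears only in footnotes. SAP 8.2.4 does not state it, and SAP 6.4 calls these analyses exploratory. That is fair, and it makes a superiority footnote on those rows harder to justify. Much of the subgroup error is ordinary multiplicity and would arise without any dose selection.

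Pooling is openly planned in Protocol 10.2 and SAP 6.1. What is absent is any caution that the pooled estimate includes the data that chose the dose.

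**Conclusion.** The contradiction is in the text and needs no modelling: no testing and so no adjustment, beside a superiority rule on unadjusted intervals. Confidence in it and in the direction of the error is high; confidence in the size is moderate, because DOOR rates, selection noise, the count model and subgroup prevalences are all assumed.

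With inert doses, a false overall statement occurs in about 2-4% of trials under loosely outcome-linked selection and up to about 5% under a mechanical pick, against about 2-2.5% with no selection. Across the five distinct comparisons the figure is about 6-12%, and about 4.5-9% even without a selection effect. The pooled DOOR probability moves up by about 0.4-2.3 points, at most about 3.3.

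A reader might infer that pooling makes the estimate or its interval unusable, or that selection doubled the error rate in this trial. Neither is supported. The shift is small against a half-width of 14-15 points, and two-sided coverage stays near 95%. Near-doubling needs a mechanical pick on DOOR, whereas the addendum describes a judgement that also weighed safety. This should be corrected, but it does not undermine the trial's descriptive results.

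**What to change.** - Delete the superiority sentence in SAP 8.1.3 and 8.1.3.1, and the superiority footnotes in Tables 26 and 29 and addendum Tables 14, 15, 18 and 19.
- Keep the pooled DOOR probability and 95% CI, labelled for example: *Descriptive. Stage 2a data were used to choose the dose and are included, so the estimate may favour bacteriophage.* Label the subgroup CIs descriptive too.
- Report the Stage 2b-only DOOR probability and 95% CI beside the pooled result in Table 26/addendum Table 14.
- In SAP 8, say that CIs are used *to describe treatment effects*. State that the 50% benchmark and null-hypothesis wording in Protocol 10.2 and 10.4.2 and SAP 6.6 and 8.3 served only sample-size precision and interim planning, not a final test.

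If the sponsor prefers to keep a superiority statement, limit it to one named overall analysis and withdraw the no-testing disclaimer for that endpoint. SAP 6.5 calls IPW a sensitivity analysis and 8.1.3.1 calls it primary, so the choice must be explicit. Use Stage 2b only, or an interval adjusted for choosing one of three doses. A 98.33% interval (100 − 5/3) gave 1.2-1.8% false superiority even under a mechanical pick.

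The cost is wording and one extra column. Addendum Table 13 and Figures 19-24 already split by stage, and Listing 2 holds each subject's DOOR category. The Stage 2b-only CI is wider: at an estimate of 70%, about 48-49% to 85% at 12 per arm and 52-53% to 83-84% at 17. The sponsor also loses an unadjusted yes/no statement.
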